5.4.1.4. Summaries Through End of Study

Safety data through End of Study (Week 168) will be analyzed similarly to safety data through 48, replacing Week 48 with End of Study.

5.4.2. Extent of Exposure and Study Follow-up

The number and percentage of participants who receive study intervention will be summarized. Descriptive statistics for duration study intervention (N, mean, SD, median, and range (minimum, maximum)) will be summarized.

Study intervention duration is defined as (date of last dose of study intervention – date of first dose of study intervention) +1. For the placebo intervention group which has planned crossover at Week 24, the study intervention duration prior to first guselkumab dose will be summarized separately to the study intervention duration on/after first guselkumab dose.

Study follow-up duration is defined in Section 5.4.1.

Study intervention compliance will be summarized descriptively. See Section 6.6 for further details.

5.4.3. Adverse Events

The verbatim terms used in the eCRF by investigators to identify adverse events will be coded using the Medical Dictionary for Regulatory Activities (MedDRA). Any AE occurring at or after the initial administration of study intervention and those AEs that were present at baseline but worsened in severity after the start of initial study intervention are considered to be treatment emergent. If the event occurs on the day of the initial administration of study intervention, and either event time or time of administration are missing, then the event will be assumed to be treatment emergent. If the event date is recorded as partial or completely missing, then the event

will be considered to be treatment emergent unless it is known to be prior to the first administration of study intervention based on partial onset date or resolution date. All reported treatment-emergent adverse events will be included in the analysis. For each adverse event, the number and percentage of participants who experience at least 1 occurrence of the given event will be summarized by intervention group.

Summary tables will be provided for treatment-emergent adverse events:

- Treatment emergent adverse events (TEAEs)
- Treatment emergent serious AEs (SAEs)
- TEAEs with severe intensity
- TEAEs leading to permanent discontinuation of study intervention
- TEAEs related to study intervention
- SAEs related to study intervention
- TEAEs leading to dose interruption of study intervention.
- Treatment emergent infections
- Treatment emergent serious infections
- Treatment emergent infections requiring oral or parenteral anti-microbial treatment
- Injection-site reactions
- Venous thromboembolism (VTE) events
- Clinically important hepatic disorder events
- Anaphylaxis(, hypersensitivity, and serum sickness reactions
- TEAEs leading to death

All AE summary tables will include average weeks of follow-up and average number of study intervention for each intervention group.

In addition to the summary tables, listings will be provided for participants who had:

- SAEs
- TEAEs leading to permanent discontinuation of study intervention
- Anaphylactic reactions or serum sickness reactions
- Malignancies
- Serious infections including TB
- TEAEs leading to death
- VTE events
- Major adverse cardiovascular events (MACE) events

- Clinically important hepatic disorder events
- Opportunistic infections

Section 6.7 contains the methods of identification for selected AEs of interest.

A listing of participants who died will be provided, including cause of death, date of death, relationship to study intervention, and study day of death in relation to reference date.

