#### **Through Week 52**

Focusing on the pooled data (through 60 weeks for PSA3001 and through 52 weeks for PSA3002), guselkumab 100 mg SC administered at Weeks 0 and 4 and then q8w or q4w was well tolerated

in participants with active PsA through 1 year of treatment, and the guselkumab safety profile in the PsA population was generally comparable with that established in the psoriasis population.

Through 1-year, similar proportions of participants in the guselkumab q8w and q4w groups experienced adverse events (AEs), serious adverse events (SAEs), AEs leading to study discontinuation, AEs with severe intensity, infections, serious infections, and injection-site reactions. Frequencies of events of suicidal ideation, malignancy, and major adverse cardiovascular event were low and comparable in the guselkumab q8w and q4w groups. There were no events of opportunistic infections, active tuberculosis (TB), anaphylaxis or serum sickness reactions, or suicidal behavior or self-injurious behavior without suicidal intent in guselkumab-treated participants in either of the PSA3001 or PSA3002 studies through 1 year. The proportion of participants experiencing increases in transaminases was slightly higher in the guselkumab q4w group compared with the q8w group.

In addition, the number of participants with AEs, SAEs, AEs leading to discontinuation of study intervention, infections, and serious infections per 100 subject-years of follow-up were generally comparable between the guselkumab 100 mg q8w and q4w groups through 1 year and the placebo-controlled period through Week 24.

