### **Group III (n=350)**

Participants will receive SC placebo at Weeks 0, 4, 8, 12, 16, and 20, and will cross over at Week 24 to receive SC guselkumab 100 mg at Weeks 24, 28, 32, 36, 40, 44, and 48.

At Week 16, all participants in Groups I, II, and III with  $<20\%$  improvement from baseline in both tender and swollen joint counts will qualify for early escape (EE) and will be allowed to initiate or increase the dose of one of the permitted concomitant medications up to the maximum allowed dose as specified in [Table 3](#), as selected by the investigator.

At Week 48, participants who have not discontinued will be eligible to enter a long-term extension (LTE) for a period of up to approximately two years (ie, Week 48 through Week 156).

The study blind will be maintained during the LTE until the last participant has completed the Week 48 visit evaluations or discontinued prior to Week 48 and the Week 48 data base has been locked. Therefore, in order to maintain the blind, participants will continue to receive study

intervention every 4 weeks until that time. After the study is unblinded to the investigative sites, participants receiving guselkumab q8w will no longer be required to dose with placebo to maintain the blind.

Database locks (DBLs) are scheduled at Weeks 24, 48, 96, and end of study (Week 168). The first DBL will occur when all randomized participants have either completed the Week 24 assessments or terminated study participation prior to the Week 24 visit (referred to as Week 24 DBL). The second DBL will occur when all randomized participants have either completed the Week 48 assessments or terminated study participation prior to the Week 48 visit (referred to as Week 48 DBL). The third DBL will occur when all randomized participants have either completed the Week 96 assessments or terminated study participation prior to the Week 96 visit (referred to as Week 96 DBL). The fourth and final DBL will occur when all randomized participants have either completed their final safety visit or have terminated study participation.

A diagram of the study design is provided in Section 1.2, Schema.

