## **Adverse Events**

The verbatim terms used in the eCRF by investigators to identify AEs will be coded using the Medical Dictionary for Regulatory Activities (MedDRA). For each AE, the percentage of participants who experience at least 1 occurrence of the given event will be summarized by intervention group.

The following analyses of AEs will be used to assess the safety of participants:

- The incidence and type of AEs.
- The incidence and type of SAEs.
- The incidence and type of infections.
- The incidence and type of injection site reactions.

Summaries, listings, datasets, or participant narratives may be provided, as appropriate, for those participants who die, who discontinue intervention due to an AE, or who experience a severe or an SAE.

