5.4.1. Safety Tables Presentation

There are 4 DBLs in this study, respectively, at Week 24, Week 48, Week 96, and End of Study (Week 168). Depending on the safety data categories, the cumulative safety data will be analyzed through different study periods which include, but are not limited to, through Week 24, through Week 48, through Week 96, and through end of study periods. Tabular summaries of safety events for key study periods are in general presented as follows:

5.4.1.1. Summaries Through Week 24

Safety data through Week 24 will be analyzed according to the following intervention groups:

1. **Placebo:** Participants who received placebo only and no guselkumab prior to Week 24.
2. **Guselkumab 100 mg at Weeks 0, 4, and then q8w:** Participants who received guselkumab 100 mg q8w prior to Week 24 with an additional dose at Week 4.
3. **Guselkumab 100 mg q4w:** Participants who received guselkumab 100 mg q4w prior to Week 24.
4. **Guselkumab Combined:** Participants in Groups 2 and 3.

The above intervention groups 1-3 are **mutually exclusive**. This allows between-group comparisons of safety between a guselkumab group and the placebo group based on similar follow-up period in each group. The safety tables will have the column headings below:

Analysis set: Safety Analysis Set	Guselkumab			
	Placebo	100 mg q8w	100 mg q4w	Combined
	###	###	###	###

For participants who started treatment with placebo only but later received any amount of guselkumab prior to Week 24 inadvertently, the safety events/measurements on and after the first dose of guselkumab, will be excluded from the data summaries through Week 24. Only the safety events/measurements that occurred while the participants had been receiving placebo only will be included in the data summaries through Week 24.

5.4.1.2. Summaries Through Week 48

Safety data through Week 48 will be analyzed according to the following intervention groups:

1. **Placebo:** Participants who received placebo only. Follow-up will be based on the period that the participant was on placebo from the first dose up to Week 48.
 - a. For participants who started treatment with placebo and later received treatment with guselkumab (due to CO or inadvertently), follow-up will end at the first dose of guselkumab, and only the safety events/measurements that occurred prior to the first dose of guselkumab will be included in this group

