2. **Placebo → Guselkumab 100 mg q4w:** Participants who started treatment with placebo and later received treatment with guselkumab (due to CO or inadvertently). Follow-up will start from the first dose of guselkumab up to Week 48. All the safety events/measurements that occurred on and after the first dose of guselkumab up to Week 48 will be included in this group.
3. **Guselkumab 100 mg at Weeks 0, 4, and then q8w:** Participants who received guselkumab 100 mg q8w prior to Week 24 with an additional dose at Week 4. Follow-up will be from the first dose up to Week 48.

4. **Guselkumab 100 mg q4w:** Participants who received guselkumab 100 mg q4w prior to Week 24. Follow-up will be from the first dose up to Week 48.
5. **Guselkumab 100 mg q4w Combined:** Participants in Groups 2 and 4.
6. **All Guselkumab Combined:** Participants in Groups 2, 3, and 4.

The above intervention groups 1-2 are **not mutually exclusive**. The safety tables will have the column headings below:

Analysis set: Safety Analysis Set	Guselkumab					
	Placebo		100 mg q4w			All Combined
	Placebo	→	100 mg q4w	100 mg q8w	100 mg q4w	Combined
Analysis set: Safety Analysis Set	###		###	###	###	###

5.4.1.3. Summaries Through Week 96

Safety data through Week 96 will be analyzed similarly to safety data through 48, replacing Week 48 with Week 96.

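### Adverse-event tables after Week 24 show crude percentages for columns with very different follow-up and add no exposure-adjusted rate

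*SAP*

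**What the plan says.** The adverse-event metric is a crude proportion in both documents. Protocol 9.4.4 (Adverse Events) says that "the percentage of participants who experience at least 1 occurrence of the given event will be summarized by intervention group", and SAP 5.4.3 adds the count: "the number and percentage of participants who experience at least 1 occurrence of the given event will be summarized by intervention group". Neither safety section plans a rate per unit of person-time or a time-to-event summary.

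Follow-up by column in the Week 48 tables is set in SAP 5.4.1.2:

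- Placebo: for participants who go on to guselkumab, "follow-up will end at the first dose of guselkumab". Protocol 4.1 says that Group III "will cross over at Week 24 to receive SC guselkumab 100 mg", so this is about 24 weeks.
- Placebo to guselkumab: "Follow-up will start from the first dose of guselkumab up to Week 48", again about 24 weeks.
- Randomised q8w and randomised q4w, each: "Follow-up will be from the first dose up to Week 48".
- Two pooled columns: q4w Combined (crossover plus randomised q4w) and All Guselkumab Combined.

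SAP 5.4.1.3 and 5.4.1.4 reuse these columns, with Week 96 and End of Study (Week 168) in place of Week 48. The SAP also says: "All AE summary tables will include average weeks of follow-up and average number of study intervention for each intervention group".

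**The concern.** A cumulative percentage grows with time at risk. When a column followed for 24 weeks is printed beside one followed for 48, 96 or 168 weeks, identical underlying risks give different percentages, and the longer column always looks worse. Three of the four database locks produce tables of this kind.

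The issue matters most for uncommon events such as serious infections, venous thromboembolism and hepatic events. The later tables are where such events accumulate, and for them the percentage rises almost in proportion to follow-up. The pooled q4w column raises a second issue. It mixes shorter and longer follow-up and stands beside q8w, in a trial that Protocol 4.3 says will allow a relative benefit-risk assessment of q4w.

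The sponsor has used person-time for this purpose. Protocol 2.2.1.1.3 reports that adverse events, serious adverse events, discontinuations and infections in the two predecessor trials "per 100 subject-years of follow-up were generally comparable" between the two regimens through one year and the 24-week placebo-controlled period.

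**Working it through.** The documents give no figure to reproduce, so the check asks what the planned tables would show if guselkumab had no effect on the event.

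**Inputs from the documents.** Crossover at Week 24; table cut-offs at Weeks 48, 96 and 168; planned group sizes 350 placebo, 350 q8w and 250 q4w.

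**Assumptions.** A constant hazard, equal in all groups. The 24-week risk p is not in the documents and is varied from 1% to 50%. Follow-up is complete at first; attrition is added afterwards.

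**Formula.** Risk by week T is 1 − (1 − p)^(T/24). The apparent ratio to placebo is that value divided by p. Example with p = 5% at Week 96: 1 − 0.95^4 = 18.55%, and 18.55/5 = 3.71.

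| 24-week risk (placebo column) | Guselkumab, Week 48 (ratio) | Week 96 (ratio) | Week 168 (ratio) |
|---|---|---|---|
| 1% | 1.99% (1.99) | 3.94% (3.94) | 6.79% (6.79) |
| 5% | 9.75% (1.95) | 18.55% (3.71) | 30.17% (6.03) |
| 20% | 36.0% (1.80) | 59.04% (2.95) | 79.03% (3.95) |
| 50% | 75.0% (1.50) | 93.75% (1.88) | 99.22% (1.98) |

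As p approaches zero the ratio tends to T/24, so the ceilings are 2, 4 and 7.

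**Attrition.** With 20% loss per year, a 1% event gives ratios of 1.89, 3.40 and 5.12, and a 50% event gives 1.45, 1.75 and 1.81.

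**Crossover column.** At Week 48 it holds about 24 weeks, so its ratio to placebo is about 1.0. By Weeks 96 and 168 it holds up to 72 and 144 weeks.

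**q4w Combined against q8w.** Mean follow-up, with crossover time equal to T − 24:

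- Week 48: (350×24 + 250×48)/600 = 34 weeks against 48; 34/48 = 0.71.
- Week 96: (350×72 + 250×96)/600 = 82 against 96; 82/96 = 0.85.
- Week 168: (350×144 + 250×168)/600 = 154 against 168; 154/168 = 0.92.

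For uncommon events the crude percentages follow these ratios, so at equal hazards q4w Combined reads about 29% below q8w at Week 48, 15% at Week 96 and 8% at Week 168.

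**The same data as rates.** First events divided by time at risk give one value in every column at every cut-off: 2.19 per 100 participant-years when the 24-week risk is 1%, 11.15 when it is 5% and 48.5 when it is 20%. The ratio is 1.0, and attrition of 5% to 20% per year does not change it.

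**The case against.** The strongest reply is that the placebo comparison belongs elsewhere. SAP 5.4.1.1 provides separate Week 24 tables with mutually exclusive groups and presents them as the place to compare guselkumab with placebo over similar follow-up. The later tables are cumulative descriptions, no formal safety test is planned (SAP 5.4), and every adverse-event table prints average follow-up, so the imbalance is disclosed. SAP 5.4.2 also separates the placebo arm's duration before and after crossover. All of this stands, and it limits the consequence. It does not remove the point. A mean follow-up is not a rate: it has no interval, does not stop at the first event and cannot be used to rescale common events linearly. The Week 24 tables also cannot cover events that accumulate later, and they do not contain the pooled q4w column.

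A reader might infer that the comparison of q4w with q8w is itself confounded with exposure. The documents do not support that: the two randomised columns have the same planned window at each lock. Only the pooled column distorts the dose comparison.

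A reader might also infer that percentages should give way to rates. Protocol 2.2.1.1.3 reports similar proportions first and adds the subject-year figures to them. That is a precedent for adding rates, not for demoting percentages.

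**Conclusion.** The point holds as a presentational weakness in the later safety tables. Under a constant, equal hazard and complete follow-up, the spurious guselkumab-to-placebo ratio is at most 2 at Week 48. For events with a 24-week risk of 1% to 5% it is about 3.7 to 3.9 at Week 96 and 6.0 to 6.8 at Week 168. With 20% yearly attrition the Week 168 figure for a 1% event falls to about 5.1.

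It would be too strong to say that equal risks will look several-fold different throughout. That cannot happen at Week 48, and for events with a 24-week risk near 50% the ratio stays below 2 at every cut-off. The Week 168 values also need participants who remain to the end; those who do not enter the extension have their last safety visit around Week 60.

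The hazards, 24-week risks and attrition are assumptions. Rates remove the effect of follow-up length, but not that of hazards that change over time or of selective retention, which is a further reason to keep the Week 24 tables as the main placebo comparison. Efficacy conclusions are unaffected.

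**What to change.** In SAP 5.4.3, for the Week 48, Week 96 and End of Study tables:

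- Keep the crude percentages and the average follow-up.
- Add, by column, incidence per 100 participant-years with a 95% confidence interval, counting time to the first event or to the end of that column's follow-up. Do this for treatment-emergent adverse events, serious adverse events, infections, serious infections, venous thromboembolism and clinically important hepatic events.
- Add one short table of the same rates for malignancy and major adverse cardiovascular events, which SAP 5.4.3 now covers only by listings.
- State that comparisons with placebo rest primarily on the Week 24 tables, and that the dose comparison uses the randomised q4w and q8w columns, not q4w Combined.

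The cost is modest programming and a few more table rows. First-event times must be derived as well as follow-up weeks, but no new data are needed.

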5.4.4. Additional Safety Assessments

5.4.4.1. Clinical Laboratory Tests

Clinical laboratory tests will be displayed for the participants included in the safety analysis set.

The clinical laboratory parameters to be evaluated by the central laboratory include but are not limited to:

- **Hematology:** basophils, eosinophils, hemoglobin, hematocrit, lymphocytes, monocytes, neutrophils, platelets, red blood cell (RBC) count and white blood cell (WBC) count
- **Clinical chemistry:** albumin, alkaline phosphatase (ALP), alanine aminotransferase (serum glutamate pyruvate transaminase) [ALT (SGPT)], aspartate aminotransferase (serum glutamic oxaloacetic transaminase) [AST (SGOT)], bicarbonate, blood urea nitrogen (BUN), calcium, chloride, creatinine, glucose, potassium, sodium, total bilirubin, and total protein

Due to the Major Disruption resulting from the conflict involving Ukraine and neighboring countries/territories beginning February 24, 2022, central labs were unavailable for some sites over a period of time. In these instances, local labs, limited to the following parameters, may have been entered into the eCRFs: sodium, potassium, chloride, bicarbonate, BUN, creatinine, total bilirubin, direct bilirubin (conditionally), indirect bilirubin (conditionally), AST, ALT, GGT, ALP, and LDH. Certain analyses will use central lab data only, while other analyses may use a combination of central lab data and local lab data.

Descriptive statistics and graphical displays of observed values and changes from baseline will be presented for selected chemistry and hematology laboratory tests at scheduled time points. Only central lab data will be used for this analysis.

Shift tables from baseline to post-baseline will be produced for select laboratory parameters. Both central and local lab data will be used for this analysis.

Abnormality criteria based on toxicity grade will be applied to baseline and postbaseline values using National Cancer Institute's Common Terminology Criteria for Adverse Events (NCI-CTCAE) for parameters with NCI-CTCAE criteria defined. Applicable laboratory results will be graded according to NCI-CTCAE version 5.0. Both central and local lab data will be used for this analysis. Abnormality for selected chemistry and hematology laboratory tests will be summarized by study intervention for:

- Number and percent of participants with post-baseline values by maximum toxicity grade

- Listings of participants with any post-baseline lab value of NCI-CTCAE toxicity Grade 3 or higher

Number and percent of participants with post-baseline elevated liver chemistry tests will also be produced using both central and local lab data, for

ALT categories:

- $>1x$ to $<3x$ Upper limit of normal (ULN)
- $\geq 3x$ to $<5x$ ULN
- $\geq 5x$ to $<8x$ ULN
- $\geq 8x$ ULN

AST categories

- $>1x$ to $<3x$ ULN
- $\geq 3x$ to $<5x$ ULN
- $\geq 5x$ to $<8x$ ULN
- $\geq 8x$ ULN

Total Bilirubin categories:

- $>1x$ to $<2x$ ULN
- $\geq 2x$ ULN

ALP categories:

- $>1x$ to $<2x$ ULN
- $\geq 2x$ to $<4x$ ULN
- $\geq 4x$ ULN

Both central and local lab data will be used for this analysis.

A listing of participants with ANY of post-baseline ALT $\geq 3x$ ULN, AST $\geq 3x$ ULN, ALP $\geq 2x$ ULN, OR total bilirubin $\geq 2x$ ULN will be created. Additionally, they will be assessed for the following two combined criteria:

- 1) Total bilirubin ≥ 2 xULN within 5 days after either ALT or AST ≥ 3 xULN
- 2) International normalized ratio (INR) >1.5 within 5 days after either ALT or AST ≥ 3 xULN

Number and percent of participants who met each of the following 5 liver function criteria individually, as well as overall (i.e, met any of the 5), as determined by the investigator, will be summarized:

- **ALT or AST absolute:**
ALT or AST ≥ 8 xULN
- **ALT or AST increase:**
ALT or AST ≥ 5 xULN but <8 xULN persists for ≥ 2 weeks, OR
ALT or AST ≥ 3 xULN but <5 xULN persists for ≥ 4 weeks
- **Bilirubin or INR:**
ALT or AST ≥ 3 xULN **and** total bilirubin ≥ 2 xULN, OR
ALT or AST ≥ 3 xULN **and** INR >1.5
- **Cannot monitor:**
ALT or AST ≥ 5 xULN but <8 xULN and cannot be monitored weekly for ≥ 2 weeks, OR
ALT or AST ≥ 3 xULN but <5 xULN and cannot be monitored weekly for ≥ 4 weeks
- **Symptomatic:**
ALT or AST ≥ 3 xULN associated with symptoms (new or worsening) believed to be related to liver injury or hypersensitivity

